10.3.3. Other Analyses

Saliva:

AUC(0- ∞)	Area under the concentration-time curve from time 0 (predose) extrapolated to infinite time
AUC(0-t)	Area under the concentration-time curve from time 0 (predose) to time of last quantifiable concentration
C _{max}	Maximum observed concentration
λ_z	Terminal-phase rate constant
t _{1/2}	Terminal phase half life

T _{max}	Time to first occurrence of C _{max}
CL/F	Apparent oral clearance
V _z /F	Apparent volume of distribution
RAUC(0-t)	The ratio of the AUC(0-t) observed in saliva relative to the unbound AUC(0-t) in plasma, calculated as: $RAUC(0-t) = \frac{AUC(0-t)_{saliva}}{unbound\ AUC(0-t)_{plasma}}$
RAUC(0-∞)	The ratio of the AUC(0-∞) observed in saliva relative to the unbound AUC(0-∞) in plasma, calculated as: $RAUC(0-∞) = \frac{AUC(0-∞)_{saliva}}{AUC(0-∞)_{plasma}}$

Saliva concentrations of gepotidacin and the associated PK parameters will be listed, and summary statistics (n, mean, median, SD, minimum, maximum, and CV) will be presented by time point and group. Mean and individual saliva concentration versus time profiles will be presented graphically on linear and semilogarithmic scales.

The natural log-transformed saliva AUC(0-∞) and C_{max} values for gepotidacin in the hepatic impairment groups and normal hepatic function groups will be compared using an analysis of variance. Geometric mean ratios between hepatic impairment groups and normal hepatic function groups, and 90% CIs for the ratios of AUC(0-∞) and C_{max} for gepotidacin will be presented.

An exploratory analysis will be performed to explore the relationship between saliva and unbound plasma concentrations. Natural log-transformed saliva gepotidacin concentrations versus the natural log-transformed plasma gepotidacin concentrations will be plotted and a regression line will be fitted. A similar analysis will also be performed for the AUC(0-∞), AUC(0-t), and C_{max}.

Detailed descriptions of the analyses in this study will be presented in the RAP.

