7.2.1.2. Derived Pharmacokinetic Parameters

Pharmacokinetic parameters will be calculated by standard non-compartmental analysis according to current working practices and using the currently supported version of WinNonlin. All calculations of non-compartmental parameters will be based on actual sampling times.

Plasma pharmacokinetic parameters listed below will be determined from the total plasma concentration-time data, as data permits.

Parameter	Parameter Description
AUC(0-t)	Area under the concentration-time curve from time 0 (predose) to time of last quantifiable concentration, to be calculated using the linear trapezoidal rule for each incremental trapezoid and the log trapezoidal rule for each decremental trapezoid
Tmax	Time to first occurrence of Cmax
tlag	Lag time before observation of drug concentrations in sampled matrix
t _{1/2}	Terminal half-life will be calculated as: $t_{1/2} = \ln 2 / \lambda_z$
λ_z	Terminal-phase rate constant
CL/F	The apparent oral clearance, calculated as: $CL/F = \text{Dose} / AUC(0-\infty)$
Vz/F	The apparent volume of distribution during the terminal phase, calculated as: $V_z/F = CL / \lambda_z$

NOTES:

- Additional parameters may be included as required.
- For the derivation of unbound plasma PK parameters; the total plasma PK parameters AUC(0-t) will be multiplied by 0.67, and the total plasma PK parameter CL/F will be divided by 0.67, to correct for the low plasma protein binding of gepotidacin (33%) observed in previous studies.

Pharmacokinetic parameters listed will be determined from the urine concentration-time data, as data permits.

Parameter	Parameter Description
Ae total	Total unchanged drug (total amount of drug excreted in urine), calculated by adding all the fractions of drug collected over all the allotted time intervals
Ae(t1-t2)	Amount of drug excreted in urine in time intervals for predose, 0 to 6, 6 to 12, 12 to 24, 24 to 36, and 36 to 48 hours after dosing for subjects with hepatic impairment; and predose, 0 to 2 hours, 2 to 4 hours, 4 to 6 hours, 6 to 8 hours, 8 to 12 hours, 12 to 24 hours, 24 to 36 hours, and 36 to 48 hours for subjects with normal hepatic function; calculated by multiplication of the urine concentration for a time interval and the length of this time interval.

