7.3.1.2. Derived Pharmacokinetic Parameters

Pharmacokinetic parameters will be calculated by standard non-compartmental analysis according to current working practices and using the currently supported version of WinNonlin. All calculations of non-compartmental parameters will be based on actual sampling times. Pharmacokinetic parameters listed will be determined from the saliva concentration-time data, as data permits.

Parameter	Parameter Description
AUC(0-t)	Area under the concentration-time curve from time 0 (predose) to time of last quantifiable concentration, to be calculated using the linear trapezoidal rule for each incremental trapezoid and the log trapezoidal rule for each decremental trapezoid.
AUC(0-∞)	Area under the concentration-time curve from time 0 (predose) extrapolated to infinite time, calculated as: $AUC(0-\infty) = AUC(0-t) + C(t) / \lambda_z$
C _{max}	Maximum observed concentration, determined directly from the concentration-time data.
T _{max}	Time to first occurrence of C _{max}
t _{1/2}	Terminal phase half-life will be calculated as: $t_{1/2} = \ln 2 / \lambda_z$
λ _z	Terminal-phase rate constant
CL/F	The apparent oral clearance, calculated as: $CL/F = Dose / AUC(0-\infty)$
V _z /F	The apparent volume of distribution during the terminal phase, calculated as: $V_z/F = CL / \lambda_z$
RAUC(0-t)	The ratio of the AUC(0-t) observed in saliva relative to the unbound AUC(0-t) in plasma, calculated as: $RAUC(0-t) = AUC(0-t) \text{ saliva} / AUC(0-t) \text{ plasma}$
RAUC(0-∞)	The ratio of the AUC(0-∞) observed in saliva relative to the unbound AUC(0-∞) in plasma, calculated as: $RAUC(0-\infty) = AUC(0-\infty) \text{ saliva} / AUC(0-\infty) \text{ plasma}$

NOTES:

- Additional parameters may be included as required.
- Since plasma protein binding of gepotidacin is low (33%), only total plasma drug concentrations and total plasma PK parameters will be reported for the plasma PK analysis. However, to derive the saliva to unbound plasma AUC(0-t) and AUC(0-∞) ratios, a correction factor of 0.67 will be applied to the total plasma AUCs of gepotidacin to derive the unbound plasma AUCs.

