10.7. Appendix 7: Abbreviations & Trade Marks

10.7.1. Abbreviations

Abbreviation	Description
ADaM	Analysis Data Model
AE	Adverse Event
Ae(t1-t2)	Amount of drug excreted in urine in a time intervals
Ae total	Total unchanged drug (total amount of drug excreted in urine)
AUC(0-∞)	Area under the concentration-time curve from time 0 (predose) extrapolated to infinite time
AUC(0-t)	Area under the concentration-time curve from time 0 (predose) to time of last quantifiable concentration
AUC(0-12)	Partial area under the curve estimated from urine concentrations samples collected from predose to 12 hours post dose
AUC(0-24)	Partial area under the curve estimated from urine concentrations samples collected from predose to 24 hours post dose
AUC(0-48)	Partial area under the curve estimated from urine concentrations samples collected from predose to 48 hours post dose
BMI	Body mass index
CDISC	Clinical Data Interchange Standards Consortium
CI	Confidence Interval
CL/F	Apparent oral clearance
CLr	Renal clearance of drug
Cmax	Maximum observed concentration
CVb	Coefficient of Variation (Between subjects)
DP	Decimal Places
ECG	Electrocardiogram
eCRF	Electronic Case Record Form
fe%	Percentage of the given dose of drug excreted in urine
FDA	Food and Drug Administration
GSK	GlaxoSmithKline
IA	Interim Analysis
ICH	International Conference on Harmonisation
IDSL	Integrated Data Standards Library
PCI	Potential Clinical Importance
PK	Pharmacokinetic(s)
QTcF	Frederica's QT Interval Corrected for Heart Rate
QTcB	Bazett's QT Interval Corrected for Heart Rate
RAP	Reporting & Analysis Plan
RAUC(0-t)	The ratio of the AUC(0-t) observed in saliva relative to the AUC(0-t) in plasma
RAUC(0-∞)	The ratio of the AUC(0-∞) observed in saliva relative to the AUC(0-∞) in plasma
SAC	Statistical Analysis Complete
SDTM	Study Data Tabulation Model
t1/2	Terminal phase half life

Abbreviation	Description
λ_z	Terminal-phase rate constant
TFL	Tables, Figures & Listings
t _{lag}	Lag time before observation of drug concentrations in sampled matrix
T _{max}	Time to first occurrence of C _{max}
V _z /F	Apparent volume of distribution of the terminal phase

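### SAP 7.3.1.2 defines RAUC against unbound plasma AUC, but both printed formulas omit the 0.67 factor and, taken literally, give ratios 33% too low

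*SAP*

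**What the plan says.** RAUC(0-t) and RAUC(0-∞) are secondary saliva endpoints under the exploratory objective. Both the protocol (section 4) and the SAP (section 2.2) describe them as ratios of saliva to unbound plasma AUC.

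Within the parameter table of SAP 7.3.1.2:

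- **Definition.** The RAUC(0-t) row reads "The ratio of the AUC(0-t) observed in saliva relative to the unbound AUC(0-t) in plasma, calculated as". The RAUC(0-∞) row has the same construction.
- **Formula.** Each row then divides saliva AUC by plasma AUC, with neither *unbound* nor 0.67 in the denominator.
- **Note under the table.** It begins "Since plasma protein binding of gepotidacin is low (33%), only total plasma drug concentrations and total plasma PK parameters will be reported" and goes on to say that, for these ratios, "a correction factor of 0.67 will be applied to the total plasma AUCs of gepotidacin to derive the unbound plasma AUCs".

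Elsewhere:

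- **SAP 10.7.1 (abbreviations)** gives RAUC(0-t) as "The ratio of the AUC(0-t) observed in saliva relative to the AUC(0-t) in plasma". RAUC(0-∞) is worded likewise. The protocol's abbreviation list keeps *unbound* for both.
- **Protocol 9.5.4** sets the 0.67 rule for both ratios.
- **Protocol 10.3.3** writes *unbound* in its RAUC(0-t) formula. Its RAUC(0-∞) entry is introduced as "The ratio of the AUC(0-∞) observed in saliva relative to the unbound AUC(0-∞) in plasma, calculated as", but the formula that follows has plain plasma AUC.

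**The concern.** A derivation table is what a programmer works from, and here the formula and its own definition give different values. The SAP makes the slip easier to act on because it creates two versions of plasma AUC: the total values, and unbound values obtained by multiplying by 0.67 (notes in 7.1.1.2 and 7.2.1.2). It also plots saliva against each (7.3.4.1; Figures 3.10 to 3.13). Both versions will therefore exist, and the formula does not say which one to use.

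The omission does not look deliberate. SAP Table 1 (section 2.1) lists one departure from the protocol's analysis plan, and it concerns hypersensitivity listings.

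What is at stake is the reported level of RAUC in the saliva parameter summary (Table 3.6) and listing (Listing 46), both due at the interim and the final analysis. Labels taken from the abbreviation list would also misdescribe the quantity, even if the calculation were right.

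**Working it through.** **Inputs**

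| Item | Value | Source |
|---|---|---|
| Plasma protein binding | 33% | SAP 7.3.1.2 note; protocol 9.5.4 |
| Correction factor | 0.67 | SAP 7.3.1.2 note; protocol 9.5.4 |
| Denominator in words | unbound plasma AUC | SAP 7.3.1.2 |
| Denominator in formula | plasma AUC, unqualified | SAP 7.3.1.2 |

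**Step 1: the plan's own figure.** Unbound fraction = 1 − 0.33 = 0.67. This reproduces the stated factor exactly, so the factor itself is not in question.

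**Step 2: what an unqualified plasma AUC means.** SAP 7.2.1.2 says "Plasma pharmacokinetic parameters listed below will be determined from the total plasma concentration-time data", and AUC(0-t) is in that list. SAP 7.1.1.1 says that only total plasma drug is measured. The unqualified symbol is therefore the total AUC.

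**Step 3: the two readings.**

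- By definition and note: RAUC = AUC saliva / (0.67 × AUC plasma, total)
- By formula as printed: RAUC = AUC saliva / AUC plasma, total
- Printed / defined = 0.67 for any AUC values: 0.67 − 1 = −33%
- Defined / printed = 1/0.67 = 1.4925: +49.3%

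**Step 4: illustrations.** The AUC values below are invented, in arbitrary units.

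| Saliva AUC | Total plasma AUC | As printed | As defined |
|---|---|---|---|
| 20 | 20 | 1.00 | 1.49 |
| 10 | 30 | 0.333 | 0.498 |
| 35 | 25 | 1.40 | 2.09 |

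**Step 5: what moves and what does not.** On the log scale the slip is a constant shift of ln(0.67) = −0.400. A geometric mean of RAUC and its confidence limits are all multiplied by 0.67. The SD of the logged values, and so the between-subject CV defined in SAP 10.3.3, does not change. A between-group ratio does not change either. With one group at 10/30 and another at 12/28, the printed formula gives (10/30)/(12/28) = 0.778. The defined formula gives [10/(0.67×30)]/[12/(0.67×28)] = 0.778.

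**Step 6: a neighbouring wording slip.** In SAP 7.3.4.1 the endpoint line names saliva AUC(0-∞), Cmax and Tmax, but the ANOVA line says that plasma AUC(0-∞) and Cmax will be compared. Table 3.9, the corresponding display, is a saliva analysis.

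**The case against.** The best reply is that the intent is already settled. Each RAUC row says *unbound* in the sentence that leads into its formula, and the note directly below names both ratios and applies 0.67. The protocol and SAP endpoint tables, the protocol's abbreviation list and protocol 9.5.4 all say the same, and no text tells anyone to use total AUC. A wrong number needs a programmer who follows the formula and disregards the words on either side of it. This stands: it makes the error less likely and the point a minor one. It does not make the printed formulas right.

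Two stronger readings are tempting, and neither is supported.

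- **That RAUC(0-t) and RAUC(0-∞) would end up on different scales.** A reader might infer this from the protocol's two formulas, one with *unbound* and one without. The SAP writes its two formulas alike, so literal programming from the SAP treats both the same way. A mismatch would require programming from the protocol while ignoring both the words that introduce its RAUC(0-∞) formula and the rule in 9.5.4, which covers both ratios.
- **That a conclusion about saliva reflecting free drug would change.** A reader might set RAUC against 1. The documents give no such reference value, no criterion, and no conclusion that depends on the level of RAUC. SAP 7.3.4.1 does not model RAUC, and Table 3.9 is restricted to AUC(0-∞) and Cmax.

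**Conclusion.** The point holds as a wording error in a derivation formula. Both SAP formulas for RAUC contradict their own definitions and the note beneath them, and the abbreviation list repeats the omission. If programmed as printed, each ratio is 0.67 of the defined value.

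The reach is narrow. Only the absolute level of an exploratory, descriptive endpoint is exposed. Between-group ratios of RAUC, the plasma and urine analyses, and the decision to proceed to Part 2 are untouched.

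This rests on two assumptions. The first is that unqualified plasma AUC means total, which follows from SAP 7.1.1.1 and 7.2.1.2 although the formulas do not say so. The second is that the same formula, with the plan's single 0.67, is used in every group, which is why the constant cancels in between-group ratios.

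**What to change.** In the SAP:

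1. In 7.3.1.2, write both formulas as AUC saliva / (0.67 × total AUC plasma), using the matching AUC(0-t) or AUC(0-∞).
2. In 10.7.1, restore *unbound* before the plasma AUC in both RAUC entries.
3. In the ANOVA line of 7.3.4.1, change plasma to saliva so that it matches the endpoint line above it and Table 3.9.

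The cost is a few words, with no change to data, design or sample size. The protocol's RAUC(0-∞) formula in 10.3.3 can be aligned whenever the protocol is next amended. It does not justify an amendment of its own, because protocol 9.5.4 already sets the 0.67 rule.

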7.3.2. Summary Measure

Area under concentration-time curve (AUC[0-∞]) and Cmax following single doses of gepotidacin in subjects with normal hepatic function and hepatically impaired subjects.

7.3.3. Population of Interest

The primary pharmacokinetic analyses will be based on the PK population for saliva PK concentrations and the PK parameter population for saliva PK parameters and statistical analysis, unless otherwise specified.

7.3.4. Statistical Analyses / Methods

Details of the planned displays are provided in [Appendix 8: List of Data Displays](#) and will be based on GSK Data Standards and statistical principles.

Unless otherwise specified, endpoints/variables defined in Section 7.3.1 will be summarized using descriptive statistics, graphically presented (where appropriate) and listed.

7.3.4.1. Statistical Methodology Specification

The following pharmacokinetic statistical analyses will only be performed if sufficient data is available (i.e. if participants have well-defined saliva profiles).

Endpoints

 Saliva exploratory pharmacokinetic (PK) endpoints include AUC(0-∞), Cmax, and Tmax of gepotidacin, as data permit.
Model Specification

 The plasma ln-transformed AUC(0-∞) and Cmax values for gepotidacin in the hepatic impairment groups and the normal hepatic function group will be compared using an analysis of variance (ANOVA). Saliva Tmax will be analyzed non-parametrically using the Mann Whitney U test (Wilcoxon rank sum test). The point estimates and 90% CI for the median differences will be derived for hepatic impairment and healthy participants based on Hodges-Lehmann estimation.
Model Checking & Diagnostics

 Model assumptions will be applied, but appropriate adjustments may be made based on the data.
Model Results Presentation

 Statistical analysis by ANOVA will be presented in tabular format with geometric mean ratios between hepatic impairment groups and normal hepatic function group, and 90% CIs for the ratios of AUC(0-∞), Cmax, and AUC(0-48) for gepotidacin. Scatter plots of natural ln-transformed saliva gepotidacin concentrations versus the natural ln-transformed unbound and total plasma gepotidacin concentrations will be plotted and a regression line will be fitted. Scatter plots of natural ln-transformed saliva gepotidacin PK parameters versus the natural

In-transformed unbound and total plasma gepotidacin PK parameters will also be performed for the AUC(0-∞), AUC(0-t), C_{max}, CL/F, and t_{1/2}.

- The point estimates and 90% confidence intervals for the median differences in T_{max} will be calculated for the cohort difference (hepatically impaired – healthy participants).

8. SAFETY ANALYSES

The safety analyses will be based on the Safety population, unless otherwise specified.

8.1. Adverse Events Analyses

Adverse events analyses including the analysis of adverse events (AEs), Serious (SAEs) and other significant AEs will be based on GSK Core Data Standards. The details of the planned displays are provided in [Appendix 8: List of Data Displays](#).

8.2. Adverse Events of Special Interest Analyses

Liver monitoring/stopping events and cardiovascular events will be considered AEs of Special Interest (AESIs). AESIs are flagged in the eCRF and details of events are collected on special eCRF pages. The details of the planned displays are provided in [Appendix 8: List of Data Displays](#).

8.3. Clinical Laboratory Analyses

Laboratory evaluations including the analyses of Chemistry laboratory tests, Hematology laboratory tests, Urinalysis, and liver function tests will be based on GSK Core Data Standards. Division of Microbiology and Infectious Diseases (DMID) grading for all parameters as specified in the protocol will be assigned programmatically by PPD in the Laboratory Analysis Dataset. DMID grading will be applied for all subjects, regardless of hepatic impairment. The details of the planned displays are in [Appendix 8: List of Data Displays](#).

8.4. Other Safety Analyses

The analyses of non-laboratory safety test results including ECGs and vital signs will be based on GSK Core Data Standards, unless otherwise specified. The details of the planned displays are presented in [Appendix 8: List of Data Displays](#).

10. APPENDICES

10.1. Appendix 1: Schedule of Activities

10.1.1. Protocol Defined Time and Events Table

Procedure ¹	Screening (up to 30 days prior to Day -1)	Check- in -1	Treatment Period (Days)			Follow-up (10 [±5] days postdose) or Early Termination	Notes
			1	2	3		
Confined to clinic		X	X	X	X		Participants will be admitted to the clinic on Day -1 and will be discharged on Day 3. Confinement will be 4 days and 3 overnight stays
Informed consent	X						
Inclusion and exclusion criteria	X	X					Recheck clinical status before enrollment and/or study drug administration
Demographics	X						
Complete physical examination including height and weight	X						
Abbreviated physical examination		X			X	X	
Medical history (includes substance usage and history of hepatic disease)	X						Substances: drugs, alcohol, and caffeine. Participants with hepatic impairment should be on a stable regimen of chronic medications 7 days before study drug administration on Day 1
Past and current medical conditions (including hepatic impairment medical history, Child-Pugh score, and Clcr)	X						Child-Pugh as defined in the FDA Guidance for Industry: Pharmacokinetics in Patients with Impaired Hepatic Function [DHHS 2003]
Pregnancy test	X	X				X	Urine (or serum) pregnancy test (if WOCBP), as appropriate (see Protocol, Table 5)

Procedure ¹	Screening (up to 30 days prior to Day -1)	Check- in -1	Treatment Period (Days)			Follow-up (10 [±5] days postdose) or Early Termination	Notes
			1	2	3		
FSH	X						Estradiol and FSH at Screening (for women of non-childbearing potential), as appropriate (see Protocol, Table 5)
HIV antibody, hepatitis B surface antigen, and hepatitis C antibody testing	X						If test has otherwise been performed within 3 months before study drug administration, testing at Screening is not required
Drug and alcohol screen	X	X					See Protocol, Table 5
Laboratory assessments (include liver chemistries)	X	X		X		X	Including serum chemistry, hematology, and urinalysis. Results from 24 hours after dosing should be available before discharge on Day 3
12-lead ECG	X	X	X	X	X	X	See Section 10.1.2 for timing of assessments
Vital signs	X	X	X	X	X	X	Respiratory rate and body temperature collected at Screening only See Section 10.1.2 for timing of assessments
Genetic sample		X					Informed consent for optional substudies (e.g., genetics research) must be obtained before collecting a PGx sample. The PGx sample can be collected anytime, but Day -1 is recommended
Study drug administration			X				
Blood collection for pharmacokinetics			X	X	X		See Section 10.1.2 for time points

Procedure ¹	Screening (up to 30 days prior to Day -1)	Check- in -1	Treatment Period (Days)			Follow-up (10 [±5] days postdose) or Early Termination	Notes
			1	2	3		
Urine collection for pharmacokinetics			X	X	X		Participants with normal hepatic function and participants with hepatic impairment will have different collection intervals See Section 10.1.2 for time points
Saliva collection for pharmacokinetics			X	X	X		See Section 10.1.2 for time points
AE/SAE review	X	X	←-----→			X	
Concomitant medication review		X	←-----→			X	

AE = adverse event, Clcr = estimated creatinine clearance; ECG = electrocardiogram, FDA = Food and Drug Administration; FSH = follicle-stimulating hormone; HIV = human immunodeficiency virus; PGx = pharmacogenetic, SAE = serious AE; WOCBP = women of childbearing potential.

¹ When coinciding with safety and/or pharmacokinetic assessments, electrocardiograms, vital signs, and pharmacokinetic blood collections should be performed in said order.

